## **1. Annotation**

There are used multiple techniques to reduce the syndrome of systemic inflammatory response, immunocorrection, and others in order to improve the results of implantation of mechanical devices, patients on the extracorporeal life-sustaining system and septic patients before surgery. Today, there are many ways to prevent the development of a systemic inflammatory response by removing leukocytes from the bloodstream by integrating a filter with a special screen in the perfusion circuit to remove leukocytes and prevent the latter from entering the systemic circulation.

The most effective approach is the method of extracorporeal hemadsorption, intended for additional therapy of patients with an increased level of cytokines in conditions of the systemic inflammatory response syndrome, in which a patient with acute pulmonary distress syndrome and cardiogenic septic shock against the background of an extracorporeal hemofiltration, an extracorporeal cytokine adsorber system was installed, intended to eliminate a wide range of inflammatory mediators, as well as multiple proteins and metabolites.

### **The purpose of the program.**

Formulation of new treatments for heart and pulmonary failure through using organ-replacing technologies.

Formulation of a clinical protocol and implementation of treatment methods into clinical practice heart and pulmonary failure using organ-replacing technologies.

### **Study design.**

Study type: interventional (clinical study)

Set of participants: 100 participants

Distribution: randomized

Interventional model: parallel

Masking: no

Primary Goal: Treatment

New methods were created for rehabilitating the function of affected organs after implantation of the LVAD, a total artificial heart, an extracorporeal life-sustaining system will be of great importance, both for Kazakhstan and for states with similar problems of donor organ deficiency, will also improve the effectiveness of surgical treatment and reduce

the level of complications and mortality of patients on the extracorporeal life-sustaining system and septic patients.

Furthermore, the results will lead to modernization and an increase in the share of innovative organ-replacing technologies in the health care system.

## **2. Explanatory note**

### **1. General information**

1.1. Name of the topic of the scientific, scientific and technical program "Development of innovative technologies for the treatment of pulmonary and heart failure to prolong human's life".

1.3. Location of the program. ~The Republic of Kazakhstan, Nur-Sultan.

1.4. Estimated start and end date of the program, its duration in months. 2021 - 2023 years, 36 months.

1.5. Organization applying for the program. Non-profit JSC "National Research Center for Cardiac Surgery".

1.6. Executors of the program. Non-profit JSC «National Research Center for Cardiac Surgery».

1.7. The requested amount of targeted program financing for the entire duration of the program is 240 265 thousand tenge, 2021 - 84 107 thousand tenge, 2022 - 84 817 thousand tenge, 2023 - 71 340 thousand tenge.

1.8. Key words characterizing the sector and the direction of the program for the selection of independent experts. Anesthesiology. Cardiothoracic surgery. Nephrology. Perfusion. Efferentology.

### **2. The general concept of the program.**

#### **2.1. Introductory part.**

Non-profit JSC «National Research Center for Cardiac Surgery» (hereinafter – Non-profit JSC "NRCCS") is a research center that implements a program for the treatment of patients with chronic heart failure (CHF) and pulmonary failure (PF) in the terminal stage, including orthotopic transplantation of the heart and lungs, mechanical support of blood circulation.

Scientific supervisor of the program - [name] - Director for Surgery and Science of the Non-profit JSC «NRCCS», Associate Professor, Doctor of Medical Sciences, cardiac surgeon of the highest category.

Scientific co-director of the program - [name] - Non-profit JSC «National Research Center for Cardiac Surgery», candidate of medical sciences, cardiac surgeon of the highest category.

The implementation of this program will improve organ recovery, reduce postoperative complications, reduce postoperative mortality and improve the quality of life of patients with pulmonary and heart failure.

## 2.2. The purpose of the program.

Development of new treatments heart and pulmonary failure using organ-replacing technologies.

Development of a clinical protocol and implementation of treatment methods into clinical practice heart and pulmonary failure using organ-replacing technologies.

## 2.3. Objectives of the program.

### **Task 1. Assessment the results of the use of extracorporeal life support systems in the treatment of pulmonary and / or heart failure.**

Subtask 1.1. Assessment of the restoration of organ function during extracorporeal life support systems using extracorporeal hemocorrection.

Subtask 1.2. Assessment of the normalization of the body's immune response and restoration of organ function during extracorporeal life support systems using an extracorporeal cytokine adsorber.

### **Task 2. Studying the restoration of organ function during implantation of the left ventricular assist device as an organ-replacing aid in heart failure.**

Subtask 2.1. Assessment of the restoration of organ function during implantation of the left ventricular assist device with the use of extracorporeal hemocorrection.

Subtask 2.2. Assessment of the normalization of the body's immune response and restoration of organ function upon implantation of the left ventricular assist device using an extracorporeal cytokine adsorber.

### **Task 3. Studying the restoration of organ function during the implantation of the total artificial heart as an organ-replacing aid in case of heart failure.**

Task 3.1. Assessment of normalization of organ function restoration during implantation of the total artificial heart with the use of extracorporeal hemocorrection.

### **Task 4. Studying the restoration of organ function during operations in conditions of the long-term cardiopulmonary bypass.**

Task 4.1. Assessment of the restoration of organ function during operations with long-term cardiopulmonary bypass, hypothermia and circulatory arrest, with the use of extracorporeal hemocorrection.

Task 4.2. Assessment of the restoration of organ function during operations with long-term cardiopulmonary bypass, hypothermia and circulatory arrest using an extracorporeal cytokine adsorber.

**Task 5. Improvement of the method of implantation of organ-replacing technologies to reduce complications in the treatment of heart and pulmonary failure.**

**3. Scientific innovativeness and significance of the program.**

Organ replacement technologies are increasingly being used in the treatment of end-stage pulmonary and heart failure to prolong human life. Severe refractory cardiogenic shock, refractory ventricular arrhythmia, active cardiopulmonary resuscitation in cardiac arrest and acute or decompensated right heart failure, sepsis, pulmonary and multiple organ failure.

Careful patient selection and consideration of possible complications are key factors in optimizing the treatment of patients in this category. Well-defined pathways for medical care to centers capable of delivering heart and lung support replacement therapy (e.g., durable ventricular assist device or heart transplant) is essential to provide high-level patient care, stabilized with extracorporeal life support, and the ability to wean from the device. Ultimately, the concentration of the most complex care in large centers of our country with developed cardiac surgery and anesthetic capabilities can be a way to significantly improve the care of this group of patients.

Despite advances in mechanical ventilation, severe acute pulmonary distress syndrome (APDS) is associated with high morbidity and mortality rates ranging from 26% to 58%. Extracorporeal life sustaining system is a procedure for long-term cardiopulmonary bypass and oxygen saturation of the blood outside the body, used in patients with acutely developed and potentially reversible pulmonary and / or heart failure, whose treatment does not respond to maximum standard therapy. The Heart-Lung Sustaining System is a complex network that provides oxygenation and ventilation and allows the lungs to rest and recover from pulmonary failure while minimizing the iatrogenic lung damage caused by the ventilator. In intensive care in the conditions of an extracorporeal life support system. In 2011, the National Research Center for Cardiac Surgery Non-profit JSC launched a program to provide extracorporeal life support system in Kazakhstan, and in 2016 Non-profit JSC «NRCCS» has entered to the global ELSO register (Extracorporeal Life Support Organization).

The constant increase in the number of patients with CHF is associated with both an increase in the life expectancy of patients and a decrease in mortality among patients with a complicated course of acute myocardial infarction, heart defects, etc. The most common causes leading to the development of CHF are arterial hypertension, coronary heart disease and myocardial infarction. The gold standard for treatment of patients with end-stage heart failure, tolerant to drug therapy is heart transplantation.

Deficiency of donor organs remains the most important factor holding back the development of lung and heart transplantation all over the world and in our country. Left ventricular assist device (LVAD) implantation is a bridge to heart transplantation, which improves the quality and duration of life by improving blood circulation in most patients with chronic heart failure [1]. In recent studies, it was shown that the 1-year survival rate of patients after implantation of mechanical blood circulation support devices as a "bridge to transplantation" (BTT - bridge to transplantation) was 85%, and the 2-year survival rate in patients with ventricular assist device as " final treatment "(" DT - destination therapy ") - 76% [2]. It was also noted that patients with LVAD support improve functional status and quality of life [2].

A Total Artificial Heart is a form of mechanical circulatory support in which the patient's ventricles and valves are removed and replaced with an artificial heart. Currently, a fully artificial heart is implanted in the terminal stage of biventricular heart failure as a "bridge" to heart transplantation. However, given the increasing global burden of cardiovascular disease and congenital heart disease with heart failure, the number of end-stage heart failure patients awaiting heart transplants now far outnumbers the available hearts. As a result, the use of mechanical circulatory support, including a fully artificial heart, is growing exponentially.

Sepsis, septic shock, and systemic inflammatory response syndrome are life-threatening conditions resulting from a systemic response. Dysregulation can lead to multiple organ dysfunctions [30-36].

While sepsis and septic shock are infectious in origin, systemic inflammatory response syndrome (SIRS) can also have noninfectious triggers such as open heart bypass surgery, ex vivo heart / lung perfusion, extracorporeal life support, and mechanical circulatory support. It should be noted that mortality in SIRS, septic shock and sepsis reaches 7, 16, and 40%, accordingly [37-45]. According to Sepsis-3 2016, the new definition has two categories: sepsis and septic shock [46-49]. Previous definitions of sepsis, published in 1992, have

highlighted the role of systemic inflammatory response syndrome (SIRS) as a key element in the definition of sepsis.

In order to improve the results of implantation of mechanical devices, patients on the extracorporeal life support system and septic patients before surgery, various techniques are used to reduce the syndrome of systemic inflammatory response, immunocorrection, and others. To date, there are many ways to prevent the development of a systemic inflammatory response by removing leukocytes from the bloodstream by including a filter with a special screen in the perfusion circuit to remove leukocytes and prevent the latter from entering the systemic circulation [9].

The most effective is the method of extracorporeal hemadsorption, intended for additional therapy of patients with an increased level of cytokines in conditions of the systemic inflammatory response syndrome, in which a patient with acute pulmonary distress syndrome and cardiogenic septic shock against the background of an extracorporeal system has additional life support in the circuit of the apparatus for the veno-venous hemofiltration, an extracorporeal cytokine adsorber system was installed, designed to eliminate a wide range of inflammatory mediators, as well as various proteins and metabolites [55-61].

There are some new data showing that the use of an extracorporeal cytokine adsorber for long periods of cardiopulmonary bypass surgery ( $> 120$  minutes) may be useful for preventing SIRS and reducing cytokine levels in patients have overcome by elective heart surgery [62-68].

In this study, methods will be developed to restore the function of affected organs before and / or after mechanical support of blood circulation (implantation of a completely artificial heart, implantation of an artificial left ventricle, an extracorporeal life support system) in combination with the use of an extracorporeal cytokine adsorber, which will improve the results of surgical treatment of patients with terminal heart and pulmonary failure.

New methods developed for restoring the function of affected organs after implantation of an artificial left ventricle, a completely artificial heart, an extracorporeal life support system will be of high importance, both for Kazakhstan and for states with similar problems of donor organ deficiency, will also improve the effectiveness of surgical treatment and reduce the level of complications and mortality of patients on the extracorporeal life support system and septic patients.

The clinical study data will form the basis of practical protocols for the implantation of an artificial left ventricle, a fully artificial heart, an extracorporeal life support system,

following which will improve organ recovery, reduce postoperative complications, improve the quality of life and reduce mortality after surgery.

#### **4. Research methods and ethical issues.**

All patients admitted to Non-profit JSC “NRCCS” who meet the study criteria (patients on an extracorporeal life support system, mechanical circulatory support, surgery on the aortic arch) will be included in the study after obtaining a signed informed consent. Participants will be randomized into 2 groups in a 1: 1 division.

**Intervention team # 1** using an extracorporeal hemoperfusion device Jaftron (Zhuhai Jaftron Biomedical, China) (50 patients) in subgroups: A (n = 10) - patients on extracorporeal life support systems with heart failure; B (n = 10) - patients on extracorporeal life support systems with pulmonary failure; C (n = 5) - patients with implantation of a left ventricular accessory device; D (n = 25) - during operations with prolonged artificial circulation, hypothermia and circulatory arrest.

**Intervention team # 2** using extracorporeal cytokine, CytoSorb (CytoSorbents Corporation, Monmouth Junction, NJ, USA) (50 patients) in subgroups: A (n = 10) - patients on extracorporeal life support systems in heart failure; B (n = 10) - patients on extracorporeal life support systems with pulmonary failure; C (n = 5) - patients with implantation of a left ventricular accessory device; D (n = 25) - during operations with prolonged artificial circulation, hypothermia and circulatory arrest.

#### **Retrospective analysis of patients who received a fully artificial heart.**

The duration of the intervention in each group will be 72 hours. Each Jaftron / CytoSorb Removal Column can be used within 24 hours, so all patients in 2 groups use 3 filters during the study.

Researchers will collect demographic, clinical and laboratory data from patients before, during and after surgery.

The incidence of early cellular or humoral rejection, the duration of ventilation, intensive care and hospital stay, the use of vasopressors and inotropes in the perioperative period, and the incidence of perioperative complications and survivals will be documented.

The level of cytokines (IL-1, IL-6, IL-8, IL-10, tumor necrosis factor alpha) and complements will be determined before, during and after the use of the extracorporeal life support system for heart and pulmonary failure; surgery on the aortic arch, patients on mechanical circulatory support, if investigators find a corresponding difference between the two groups in terms of clinical variables.

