### Performance evaluation criterias

| Extracorporeal life support system with pulmonary and / or heart failure |
|---|
| Primary results  |

|                          |   |
|--------------------------|---|
| 1                 | Cytokine response [Time: 24-48 hours]

The level of pro- and anti-inflammatory cytokines (IL-1, IL-6, IL-8, IL-10, tumor alpha-factor) before the implantation, 2 hours after the start of ECMO support, explantation of ECMO, 24 hours after explantation of ECMO.     |
| 2                 | SOFA-Score [Time Frame: 24, 48, 72 hours]

Sequential Organ Failure Assessment Score at 24, 48, 72 h (values from 6 to 24, where the higher values explain higher disease severity)   |
| 3                 | Difference of mean arterial pressure [Time Frame: 24, 48, 72 hours]

Comparison of mean arterial pressure at 24, 48, 72 hours between between two interventions (CytoSorb and Jafron)   |
| 4                 | Difference of CVP [Time Frame: 24, 48, 72 hours]

Comparison of CVP at 24, 48, 72 hours between between two interventions (CytoSorb and Jafron)   |
| 5                 | Serum lactate [ Time Frame: 24, 48, 72 hours ]

Level of serum lactate at 24, 48, 72 h  |
| 6                 | 
 
Days on ventilator, vasopressor and renal replacement therapy [ Time Frame: until day 30 post-surgery ]
 

Total days on ventilator, vasopressor and renal replacement therapy within 30 days post-surgery will be assessed |
| 7                 | Doses of vasopressors and / or inotropes ( $\mu\text{g} / \text{h} / \text{kg}$ bodyweight) [Time: first 72 hours]  |
| Secondary results |   |
| 1                 | Inflammatory response - The level of C-reactive protein (CRP) [Time: 24-48 hours]

The level of C-reactive protein (CRP) before the start of ECMO, 2 hours after the implantation of ECMO, during ECMO, 24 hours after ECMO explantation.                        |
| 2                 | Inflammatory response - The level of leukocytes [Time: 24-48 hours]

The level of leukocytes before the start of ECMO, 2 hours after the implantation of ECMO, during ECMO, 24 hours after ECMO explantation.   |

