| 3                 | Inflammatory response - The level of procalcitonin [Time: 24-48 hours]

The level of procalcitonin before the start of ECMO, 2 hours after the implantation of ECMO, during ECMO, 24 hours after ECMO explantation.   |
| 4                 | Level of leukocyte [Time: 24-48 hours]

Level of leukocyte cells in the bloodstream at 24, 48 hours.  |

|                          |  |
|--------------------------|--|
| 5                 | Application and dosage of vasopressors [Deadline: first 48 hours]
Incidence of application and level of dosage of vasopressors on days 2 and 3 after surgery; |
| 6                 | Application and dosage of inotropes [Deadline: first 48 hours]
Incidence of application and level of dosage of inotropes on days 2 and 3 after surgery;       |
| Long-term results |  |
| 1                 | Length of stay in the intensive care unit [Duration: first 48 hours]   |
| 2                 | Length of hospital stay [Term: up to 1 month];   |
| 3                 | 30 day survival rate.  |

| Patients with left ventricular assist device implantation |  |
|--|--|
| Primary results   |  |
| 1   | Difference of Cytokine response [Time: 24-48 hours]
Level of pro- and anti-inflammatory cytokines (IL-1, IL-6, IL-8, IL-10, tumor necrosis factor-alfa, procalcitonin)  |
| 2   | Doses of vasopressors and / or inotropes ( $\mu$ g / h / kg bodyweight)
[Deadline: first 72 hours]  |
| 3   | Renal function [Time: first 72 hours] creatinine level   |
| 4   | Lactate level [Time: first 72 hours]   |
| Secondary results   |  |
| 1   | Inflammatory response - The level of C-reactive protein (CRP) [Time: 24-48 hours]
The level of C-reactive protein (CRP) before the start of the operation, 2 hours after the start of the operation, when the operation is turned off, 24 hours after the shutdown of the operation |
| 2   | Inflammatory response - The level of leukocytes [Time: 24-48 hours]
The level of leukocytes before the start of the operation, 2 hours after the start of the operation, when the operation is turned off, 24 hours after the shutdown of the operation                             |

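### Ten primary organ-function rows name no reading before the first column and none after 72 hours, so as planned they compare levels between devices and do not measure restoration

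*Combined protocol and SAP*

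**What the plan says.** Section 2.3 sets the questions. Subtask 1.2 is "Assessment of the normalization of the body's immune response and restoration of organ function during extracorporeal life support systems", and Subtask 2.2 likewise concerns "immune response and restoration of organ function upon implantation of the left ventricular assist device". Task 4 asks about restoration of organ function in long bypass operations.

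Section 4, under the subheading on the retrospective artificial-heart analysis, states: "The duration of the intervention in each group will be 72 hours". Each column lasts up to 24 hours, "so all patients in 2 groups use 3 filters during the study". Both randomized groups receive a column; there is no untreated arm.

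The outcome tables (*Performance evaluation criterias*) then give the reading times. In the ECMO and bypass tables SOFA is "Sequential Organ Failure Assessment Score at 24, 48, 72 h", and mean arterial pressure, CVP and lactate have the same frame. In the LVAD table the row is "Lactate level [Time: first 72 hours", and creatinine has the same window. LVAD and bypass cytokines are framed at 24-48 hours. ECMO cytokines are different: "before the implantation, 2 hours after the start of ECMO support, explantation of ECMO, 24 hours after explantation of ECMO".

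*Statistical research* lists the Mann-Whitney and t-tests for quantitative data. Logistic and Cox regression are named only for categorical and survival outcomes.

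**The concern.** Restoration is a change from a patient's own starting point. With a column in both arms and no untreated control, that starting point is the only reference the trial has. If SOFA or lactate at 72 h is compared between devices with no named pre-column value, the result is a difference in level. A group that entered less ill looks the same as a group that recovered more. With 5 to 25 patients per arm in a subgroup, chance differences at entry are not small.

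A second issue is confined to cytokines. These are what the columns are described as removing. A level measured while a column is working reflects the patient's production and the column's clearance together, so a lower value need not mean a normalized response.

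The program intends to turn its results into standards and recommendations (section 9), so the wording of the conclusion matters.

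**Working it through.** **Consistency of the plan's own figures.** 72 h / 24 h per column = 3 columns, as stated. 2 x (10 + 10 + 5 + 25) = 100 patients, as stated. No power or sample-size derivation is given to reproduce.

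**Tally of the 16 primary rows** (ECMO 7, LVAD 4, bypass 5). In the bypass table the text beneath the CVP and lactate titles repeats the pressure description; I have gone by the row titles.

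| Primary rows | No. | Times named | Pre-column reading named | Extends past the column period |
|---|---|---|---|---|
| ECMO: SOFA, pressure, CVP, lactate | 4 | 24, 48, 72 h | no | no |
| Bypass: SOFA, pressure, CVP, lactate | 4 | 24, 48, 72 h | no | no |
| LVAD: lactate | 1 | first 72 h | no | no |
| LVAD: creatinine | 1 | first 72 h | no | no |
| ECMO and LVAD: drug doses | 2 | first 72 h | no | no |
| LVAD and bypass: cytokines | 2 | 24-48 h | no | no |
| ECMO: cytokines | 1 | tied to implantation and explantation | yes | yes |
| ECMO: days on support | 1 | to day 30 | not applicable | yes |

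Fourteen of 16 rows close by 72 h. The first four lines are the ten rows at issue: 4 + 4 + 1 + 1 = 10.

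**Is the last ECMO cytokine sample off-column?** The column sits in the ECMO device. Assume it starts with ECMO and stops at the earlier of 72 h and explantation. For a run of T hours, time off column at the last sample = T + 24 - min(72, T). For assumed runs of 24, 72, 120 and 240 h this gives 24, 24, 72 and 192 h. The sample is off-column in every case.

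**Chance imbalance at entry.** SD of the difference in baseline means, in SD units = sqrt(2/n):
- n = 25 per arm (bypass): sqrt(0.08) = 0.28
- n = 20 (both ECMO subgroups pooled): sqrt(0.10) = 0.32
- n = 5 (LVAD): sqrt(0.40) = 0.63

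The part that reaches 72 h is this value times the baseline-to-72 h correlation r. The protocol does not give r. For an assumed r of 0.3 to 0.7 it is 0.08 to 0.20 at n = 25, 0.09 to 0.22 at n = 20 and 0.19 to 0.44 at n = 5.

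**What adjustment gains.** With one covariate, two arms, N = 2n and normal data, adjusted variance / unadjusted variance = (1 - r^2) x (N - 3)/(N - 4).
- N = 50: factor 47/46, giving 0.93, 0.77 and 0.52 at r = 0.3, 0.5 and 0.7.
- N = 10: factor 7/6, giving 1.06, 0.88 and 0.60. Adjustment breaks even at r^2 = 1/7, that is r of about 0.38.

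**Column period.** One sentence in section 4 gives 72 hours in each group. The subgroup list in section 4 and the intervention table place the column in the operation for the bypass subgroup, and before or in the course of implantation for the LVAD subgroup. That is 2 x (5 + 25) = 60 of 100 patients. The start of the 24/48/72 h clock is not stated, and the 72 h reading falls on the boundary. If the 72 hours apply, the LVAD and bypass cytokine readings are on-column. If the column runs only in theatre, they are largely off-column. The missing pre-column reading is the same either way.

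**The case against.** The strongest reply is that the trial is randomized and compares two devices, so a comparison of levels at 24, 48 and 72 h is valid without any baseline. That stands. A reader might infer that the missing baseline biases the device comparison; it does not. Chance imbalance is already in the standard error of the test, and the loss is in precision and in what the result can be called.

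It can also be said that baselines will probably exist. Section 4 promises clinical and laboratory data from before surgery onward, *Statistical research* lists a comparison of initial data, and a window of the first 72 hours does not exclude time zero. That stands in part. None of these texts names the variables or ties a value to the ten rows, and no planned test for quantitative data uses one. The before-and-after cytokine panel in section 4 is conditional on a clinical difference being found.

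Finally, Subtask 1.2 asks about the period of extracorporeal support itself, which on-support readings address. That stands too: nothing in the plan requires a post-column reading to be the main measure for that subtask.

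**Conclusion.** The point holds for ten of the 16 primary rows. As written they give on-treatment levels by device, with no named starting value and nothing after 72 h. They cannot support a statement about restoration, and they give up precision by an amount that depends on an unstated correlation. This is worth changing but does not invalidate the randomized comparison.

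Two stronger readings are tempting and not supported. One is that all these outcomes are confounded with removal by the column. SOFA, pressure and CVP are not substances a column can remove, and although the background mentions metabolites in general, the documents do not say that lactate is adsorbed. The removal argument fits only the LVAD and bypass cytokine rows, and only if the column does run for 72 h there. No size can be put on it, because no clearance is given for either device. The other is that nothing is measured once the column is out. ECMO cytokines have a baseline and an off-column sample, and ECMO days on support run to day 30. Hospital stay and 30-day survival also run later, though they measure neither organ function nor the immune response.

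**What to change.** 1. For the ten rows, name a reading just before the first column. Compare devices on the later value adjusted for it, by ANCOVA or a rank-based equivalent, with subgroup as a factor wherever subgroups are pooled. Add no variable to a table where it is not already a primary outcome. At 5 v 5 in the LVAD group, adjustment may gain little, so show the unadjusted result beside it.
2. State the zero point of the 24/48/72 h clock, and reconcile the 72-hour statement with the descriptions of when the column is used in the LVAD and bypass groups.
3. Describe any reading taken with a column in circuit as on-treatment. For ECMO, use the existing sample 24 h after explantation as the off-column cytokine reading. For LVAD and bypass, optionally add one supportive cytokine sample about 24 h after the last column.

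The cost is small. All four subgroups already require invasive hemodynamic monitoring, so the pre-column values mean slightly more chart abstraction. The optional sample is one extra draw in 60 patients. Some patients will die before a later reading, so the plan needs a stated rule for those deaths.
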